In 1999, the ADCS launched a multi-center, randomized, double-blind, placebo-controlled, parallel trial to determine whether or not the use of vitamin E or donepezil would delay the conversion to AD in patients with MCI. Natural history data suggested that these individuals would convert to AD at a rate of 12-14% per year. The study was designed to follow subjects at six-month intervals for three years. Inclusion/exclusion criteria were developed to identify individuals with the amnestic form of MCI. Education-adjusted cut scores on logical memory were used to ensure that a true memory deficit existed and that the memory deficit was severe enough to ensure an adequate conversion rate to AD in the placebo-treated population. An adjudication committee was established to review data when a site believed that a subject had converted from MCI to AD. Biological samples for assessment purposes were collected at yearly intervals in the entire patient population, and a 25% subset underwent quantitative MRI studies at baseline, at the time of conversion, and at 36 months. A vigorous recruitment campaign was carried out and over 54,000 phone calls were handled by a centralized recruitment center. Both national and local advertising brought in 2,400 subjects for an inclinic evaluation. Seven hundred and ninety completed successful screening, and 769 were baselined for this trial at 65 sites in the U.S. and Canada. Several extremely important pieces of information have emerged from the trial.

The baseline characteristics of the subjects were reported recently and demonstrated that the criteria for amnestic MCI could be implemented in a reliable fashion on a multi-center basis (Grundman et al., 2004). The clinical performance characteristics of these subjects were intermediate between those of normal control subjects and subjects with very mild AD. In addition, the baseline MR volumetric measurements of the hippocampal formation in the

subset of subjects participating in the MRI portion of the study were almost identical to the volumetric measurements on MCI subjects published in the literature (Grundman et al., 2003).

FIGURE 1. CONVERSION FROM MCI TO AD IN THE ADCS MCI TRIAL

FIGURE 2. CONVERSION FROM MCI TO AD AS A FUNCTION OF HIPPOCAMPAL VOLUME AT BASELINE

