Scale-Revised (WMS-R) Logical Memory II, a CDR of 0.5, absence of significant enough levels of impairments in other cognitive domains so that criteria for dementia are not met, largely preserved activities of daily living, and an absence of dementia.

- a. Categorization as to amnestic MCI at screen using MMSE, logical memory and CDR.
- b. Subcategorization of amnestic MCI, single domain or multiple domain at the baseline using neuropsycological test scores by reference to the MCI flow diagram in figure 4.
- c. Mild AD: MMSE scores between 20 26 (inclusive), CDR of 0.5 or 1.0^{\,}, and meet NINCDS/ADRDA criteria for probable AD.

D.4.b.MCI

The MCI group will be the cohort of most interest. The ADCS screened 2,400 subjects for its MCI protocol: 790 MCI subjects met screening criteria and 769 were entered in our ADCS MCI trial. Using rigorous inclusion/exclusion criteria, the conversion rate to AD in this cohort was 16%/year. The most important inclusion criterion was the use of education-adjusted cutoff scores on logical memory to make certain that subjects have a true memory deficit and represent amnestic MCI, the cohort most likely to develop AD. This protocol will use almost identical inclusion criteria but will also allow the enrollment of amnestic MCI individuals with impairment in non-memory domains who do not meet clinical criteria for dementia. Exclusion criteria are less restrictive since many drugs excluded in the MCI Study may be allowed in this biomarker protocol (Grundman et al., 2004). Inclusion/exclusion criteria for AD subjects and normal controls closely match those we have previously used in other instrument or drug protocols (Aisen et al., 2003) with appropriate adjustments so that the three groups do not overlap.

For our present purposes we will focus on the amnestic subtype of MCI. Once the clinical subtype has been determined (Figure 4), then the clinician needs to address the issue of putative etiology of the syndrome. By means of the history from the participant and the study partner, the clinician then determines if the suspected etiology is of a degenerative, vascular, metabolic or other cause (Figure 5). If the suspicion is of a degenerative etiology and the clinical subtype is amnestic, then the likely outcome will be AD. The ADNI will

FIGURE 5. SUBTYPES OF MCI

MCI Subtypes

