The 95% confidence intervals for annual conversion rate and overall conversion rate through 3 years was calculated with 2 different true conversion rates (8, 12%) and two different sample sizes (300, 400). An annual drop-out rate of 10% was assumed.

N	Annual Rate (%)	3 Year Rate (%)	3 Year Rate Confidence- Interval (%)	Half-Width (%)
300	8	22.1	16.6 - 27.6	5.5
300	12	31.9	25.7 - 38.0	6.2
400	8	22.1	17.4 - 26.9	4.7
400	12	31.9	26.5 - 37.2	5.3

It can be seen from this analysis that the MCI to AD conversion rates at three years can be anticipated to have associated 95% confidence intervals with approximately half width of 5.5%. In other words the confidence interval lower and upper bounds for either annual or 3-year rates will be within 5 percentage points of the estimated annual rate in the above 4 examples.

- 2. Baseline scores on logical memory and APOE4 status will predict conversion from MCI to AD. These two predictors will be evaluated as baseline predictors of conversion using the Cox proportional hazards model. The underlying assumptions of the model will be assessed. It is anticipated that the sample size in the MCI group will be adequate to make this assessment. A power analysis based on Pearson's correlation coefficient (transformed using Fisher's Z) to assess the power to detect a univariate predictor indicates that with 400 subjects a correlation as low as 0.2 will be detected with 94% power. A correlation of 0.2 is selected as an effect size of clinical relevance.
- 3. Measures of global functioning, such as activities of everyday living, will be more sensitive than neuropsychological measure for predicting conversion from MCI to AD. Cox modeling will be used to assess the relative predictive ability of standard global and cognitive measures.
- 4. The rate of backcrossing from MCI to normal will be extremely low for this population. The backcrossing rate will be assessed using survival analysis techniques i.e. Kaplan-Meier curves. With 400 subjects, it is anticipated that it will be possible for the rates to be estimated with confidence intervals of plus or minus five percentage points (two standard deviations) based on a sensitivity analysis.

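### Protocol D.12.c item 1: the statement that conversion-rate bounds lie within 5 points is false for the 3-year rate in three of its four examples and true only of annual rates

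*Protocol*

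**What the plan says.** Hypothesis 1 (Protocol A.2 and D.12.c, item 1) is that conversion from MCI to AD averages 10-15% per year. The rate is to be estimated by Kaplan-Meier at the end of the study, and the section describes a sensitivity analysis of precision using life-table probabilities. On what was computed it states: "The 95% confidence intervals for annual conversion rate and overall conversion rate through 3 years was calculated". The four examples cross true annual rates of 8% and 12% with N=300 and N=400. On losses: "An annual drop-out rate of 10% was assumed".

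The table has one row per example, giving the 3-year rate, its 95% interval and the half-width. It has no column for an annual-rate interval. Two summary sentences follow. The first puts the 3-year half-width at about 5.5 points. The second, offered as a restatement of the first, says that the bounds "for either annual or 3-year rates will be within 5 percentage points of the estimated annual rate in the above 4 examples".

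On the earlier ADCS MCI trial, D.4.b reports that "the conversion rate to AD in this cohort was 16%/year" and adds: "This protocol will use almost identical inclusion criteria". The same paragraph qualifies this: multi-domain amnestic MCI is also admitted, and the exclusions are looser.

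**The concern.** The second summary sentence does not describe the table above it. Most of the tabulated half-widths exceed 5, the preceding sentence gives a different figure, and the reference point named for the 3-year bounds is the annual rate, which is a different quantity.

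Conversion from MCI to AD is the first outcome measure listed in the synopsis. The protocol also says that its main purpose is to inform the planning of future trials. A reader who takes the precision of the 3-year rate from the summary sentence carries away a figure that is too favourable in three of the four examples.

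**Working it through.** **Inputs**, all from D.12.c item 1: annual rate q = 8% or 12%; N = 300 or 400; annual drop-out 10%; 95% two-sided intervals, so z = 1.96. The planned MCI sample of 400 is in D.12.b.

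**Step 1. Reproduce the table.** The 3-year rate is F = 1 - (1 - q)^3, which gives 1 - 0.92^3 = 22.1% and 1 - 0.88^3 = 31.9%. With 0.9^3 = 0.729 retained at 3 years, n = 218.7 (N=300) or 291.6 (N=400). The half-width is 1.96 x sqrt(F(1 - F)/n).

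| N | q | Computed half-width | Computed interval | Tabulated half-width | Tabulated interval |
|---|---|---|---|---|---|
| 300 | 8% | 5.50 | 16.6-27.6 | 5.5 | 16.6-27.6 |
| 300 | 12% | 6.17 | 25.7-38.0 | 6.2 | 25.7-38.0 |
| 400 | 8% | 4.76 | 17.4-26.9 | 4.7 | 17.4-26.9 |
| 400 | 12% | 5.35 | 26.5-37.2 | 5.3 | 26.5-37.2 |

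All four intervals reproduce, and the half-widths agree to within rounding. The table is sound on its inputs, and its widths are those of a binomial on 3-year completers. That method is inferred from the match; the protocol does not name it.

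**Step 2. Test the sentence on the 3-year rate.** Three of the four half-widths (5.5, 6.2, 5.3) exceed 5. Rounding does not bring 6.2 or 5.5 down to 5. Their mean is (5.5 + 6.2 + 4.7 + 5.3)/4 = 5.4, so the first summary sentence (about 5.5) fits the table and the second does not.

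**Step 3. Test it as literally worded, against the annual rate.** The nearest 3-year bound is 16.6 - 8 = 8.6 points away, and the farthest is 38.0 - 12 = 26.0 points away. No 3-year bound in the table is within 5 points of the annual rate.

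**Step 4. Test it on annual rates.**
- *Constant annual rate over 3 years.* Transform each 3-year bound by 1 - (1 - F)^(1/3). The annual intervals are 5.9-10.2% and 9.4-14.7% (N=300), and 6.2-9.9% and 9.8-14.4% (N=400). Half-widths run from about 1.9 to 2.7 points.
- *Year by year, without that assumption.* Take q(1 - q)/e for each year, with e the number at risk less half of that year's drop-outs. The smallest half-width is N=400, 8%, year 1: e = 400 - 20 = 380, and 1.96 x sqrt(0.08 x 0.92/380) = 2.7. The largest is N=300, 12%, year 3: e = 176.1, and 1.96 x sqrt(0.12 x 0.88/176.1) = 4.8.

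Both ranges are below 5, so the sentence holds for annual rates.

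**Step 5. Compare with the planned estimator.** Greenwood's variance with the same drop-out, withdrawals counted at mid-interval, gives 5.1, 5.8, 4.4 and 5.0 in the table's row order (4.43 and 4.99 at N=400). The tabulated widths are therefore slightly conservative.

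**Step 6. Rates above 12%, by the table's method.** At 15% per year, F = 38.6% and the half-width is 5.59 (N=400) or 6.45 (N=300). At 16%, F = 40.7% and it is 5.64 or 6.51.

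**The case against.** The strongest reply is that little turns on this. The correct intervals stand in the table directly above the sentence, and the preceding sentence gives a fair summary. The sentence is true for annual rates. With Greenwood's variance at the planned N=400, the 3-year half-widths are 4.43 and 4.99, both under 5.

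Most of this stands and limits the size of the point. It does not rescue the sentence, which claims to hold for 3-year rates in all four tabulated examples. The tabulated values refute that. Under Greenwood both N=300 rows are still above 5 (5.1 and 5.8), and the wrong reference rate remains under any variance.

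A reader might infer four stronger things that the documents do not support:
- *That this sentence is the only precision statement for the outcome.* It is not. The table and the preceding sentence also state the precision, and they agree with each other.
- *That 16% per year is the rate the table should have been planned on.* D.4.b qualifies the similarity to the earlier trial. The 12% rate agrees with the planning figure in D.5.t, the annual rate of about 12% cited in B.3.a.ii and the 10-15% range in B.3.a.iii. Moving from 12% to 16% at N=400 changes the half-width only from 5.35 to 5.64.
- *That a true rate of 16% would put hypothesis 1 at or below the lower end of the interval.* At N=400 the annual interval would be 13.4-18.8%, which overlaps the hypothesised 10-15%.
- *That the sample size is in doubt.* D.12.b ties it to the imaging and biochemical biomarker hypotheses.

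**Conclusion.** Wrong as written. For the 3-year conversion rate the 5-point statement fails in three of four examples, contradicts the sentence before it, and uses the wrong reference rate. It is correct only for annual rates, whose intervals the text says were calculated but does not show.

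The size is modest. As tabulated, the excess over 5 is 0.3 points at N=400 and 12%, and 1.2 points at worst (N=300, 12%). This is an error in stating precision, not in the table or the design.

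The 3-year finding rests on the protocol's printed half-widths alone. The figure of 1.9 to 2.7 points for the annual rate assumes a constant annual rate over 3 years; without that assumption, year-specific half-widths are 2.7 to 4.8 points. That the table stops at 12% while hypothesis 1 reaches 15% and the earlier trial saw 16% is a gap in coverage, not an error.

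**What to change.** Delete the sentence and put in its place: *3-year conversion rate: 95% CI half-width 4.7 to 6.2 points around the estimated 3-year rate over the four examples (4.7 to 5.3 at the planned N=400); annual rate, assuming a constant annual rate over 3 years: about 1.9 to 2.7 points.*

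Use one variance method throughout and name it. Either keep the table and say that its widths are those of a binomial on 3-year completers, slightly conservative for the planned Kaplan-Meier estimate, or recompute every row by Greenwood (about 5.1, 5.8, 4.4 and 5.0) and change the replacement text to match. Figures from the two methods should not be combined in one range. An annual-interval column would supply what the text says was calculated.

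Optionally, add a row at 15-16% per year (about 5.6 points at N=400 by the table's method).

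The cost is one reworded sentence and, at most, an extra column and row. Nothing changes in design, sample size or conduct.

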Consensus Recommendations for the Postmortem Diagnosis of Alzheimer's Disease. *Neurobiology of Aging, 18*(4, Supplement 1), S1-S2.

- The Ronald and Nancy Reagan Research Institute of the Alzheimer's Association and, N. I. o. A. W. G. (1998). Consensus Report of the Working Group on: "Molecular and Biochemical Markers of Alzheimer's Disease". *Neurobiology of Aging*, 19(2), 109-116.
- Unverzagt, F. W., Gao, S., Baiyewu, O., Ogunniyi, A. O., Gureje, O., Perkins, A., et al. (2001). Prevalence of cognitive impairment: data from the Indianapolis Study of Health and Aging. *Neurology*, 57(9), 1655-1662.
- Wechsler, D. (1981). *Manual for the Wechsler Adult Intelligence Scale (rev.ed.)*. New York: The Pscyhological Corporation, Harcourt Brace Janvanovich, Inc.
- Wechsler, D. (1987). WMS-R Wechsler Memory Scale Revised Manual. New York: The Psychological Corporation, Harcourt Brace Jovanovich, Inc.

Appendix 1. CLINICAL PROTOCOL AMENDMENT 1

Summary of Amendment to Protocol

1. In efforts to provide more definitive data on the utility of obtaining longitudinal measures of CSF tau and A β in the LP subset of ADNI, consent will be obtained from the 150 ADNI participants (i.e. 50 controls, 50 MCI and 50 AD subjects) that have consented to LPs at baseline and year-1 to do a third LP at the year-2 visit.

Appendix 2. CLINICAL PROTOCOL AMENDMENT 2

Summary of Amendments to Protocol

- 1. In order to optimize the impact of the ADNI study and the CSF already collected, any participant who has had at least one Lumbar Puncture will be asked to consent to additional annual LPs. The Protocol has been updated throughout to reflect this.
- 2. Extended Follow-up of Alzheimer's Disease Subjects: Only those subjects enrolled in the primary ADNI as Alzheimer's Disease Subjects who agree to a 4th Lumbar Puncture at Month 36 will be followed for additional visits. If these subjects agree to annual LPs, they will continue to be followed with Telephone checks every 6 months and annual clinic visits with LPs. No imaging will be conducted for these subjects. Protocol has been updated throughout.
- **3.** MCI Subjects: Any MCI subject willing to continue will have annual clinic visits with 1.5 T MRI imaging. If these MCI subjects had at least one previous Lumbar Puncture, they will be asked to consent to additional annual LPs. Protocol has been updated throughout.
- **4.** Normal Controls Subjects: Any Normal Control (NL) subject willing to continue will have annual clinic visits with 1.5 T MRI imaging. If these NL subjects had at least one previous Lumbar Puncture, they will be asked to consent to additional annual LPs. If these NL subjects were randomized to the PET arm of the study, they will be asked to consent to annual PET imaging as well. Protocol has been updated throughout.
- **5.** Telephone checks will be conducted 6 months after these visits, in order to maintain contact with the subject and study partner, document any adverse events, and ensure continued interest in the ADNI study. Protocol has been updated throughout.
- 6. 3T Imaging will not be continued past the Month 36 visit.
- 7. Risks Section: Normal Control Subjects agreeing to annual PET scans will have a dose of 5mCi per scan, which will result in well below the annual limits of exposure according to the Code of Federal Regulations (21 CFR 361.1). The ADCS will continue to track radiation exposure and notify sites if dose reaches 90% of this limit.
- **8.** Overall Study Timetable: The overall timetable of the study is now extended until September 2010. At this time the ADNI 2 Protocol will be implemented and any subject willing will be enrolled for long-term follow-up.
- **9.** Appendix 1 and 2 Added to ensure changes made to the ADNI protocol are clearly defined for Research Sites and their IRBs.
